. These late sequelae are chosen by reading results from a questionnaire about late sequelae fulfilled by members of: "Danish Network for Mouth and Throat Cancer" – a community of people who have been through treatment of cancer in throat and mouth.

Participants are also asked if they have any other late sequelae.

Third objective(side effects)

Participants are at the first treatment session receiving a diary to note if they have any side-effect after treatment. At each session the therapist will ask if the participant has been experiencing any side effects and these will be noted in the participant journal and combined together so that the results contain a total overview of experienced side effects

Intervention:

The participants will receive 50 minutes of treatment of craniosacral therapy once a week in 5 weeks. The treatment will follow the protocol "avenue of expression" and step 2c and 2c in "Ten step protocol". See appendix (1)

Statistical considerations

The participants filled in the danish questionaire " Xerostomia questionnaire after minimun 3 months". The questionnaire includes a VAS xerostomia scale 0-10 (10 is worst)

The remaining 14 questions were phrased "how much does [question subject] bother you:" (translated from Danish)

not at all (1) - a little (2) - some (3) a lot (4) very much(5)

The final question(number 15) were:

"How would you feel, if you had to live the rest of your life, with the symptoms you have now?:"
enjoyable(1), very satisfied (2) neither satisfied ore unsatisfied(3), very unsatisfied(4), terrible(5)
the sum of points from the 15 questions gives an overall score.

The remaining 14 questions were phrased "how much does [question subject] bother you:" (translated from Danish)

not at all (1) - a little (2) - some (3) a lot (4) very much(5)

The final question(number 15) were:

"How would you feel, if you had to live the rest of your life, with the symptoms you have now?:"
enjoyable(1), very satisfied (2) neither satisfied ore unsatisfied(3), very unsatisfied(4), terrible(5)
the sum of points from the 15 questions gives an overall score.

This will give two scores:

the was-scale-score between 0-10 (10 is worst)

and the score for the remaining questions between 15 – 75 (75 is best)

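### The 15–75 sum score is labelled with 75 as the best value, but under the protocol's own item coding 75 is the worst possible state

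*Protocol*

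**What the plan says.** The main objective is to see whether the intervention can reduce xerostomia, using a Danish questionnaire completed at baseline, before the fifth and last treatment, and six months after treatment (Objectives; Measurement method).

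The Statistical considerations section sets out the scoring:

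- A xerostomia VAS: "The questionnaire includes a VAS xerostomia scale 0-10 (10 is worst").
- Fourteen items on how much a given problem bothers the participant, coded "not at all (1) - a little (2) - some (3) a lot (4) very much(5").
- One closing item, introduced by "The final question(number 15) were", on living with the present symptoms for life, coded "enjoyable(1), very satisfied (2) neither satisfied ore unsatisfied(3), very unsatisfied(4), terrible(5").
- The scoring rule: "the sum of points from the 15 questions gives an overall score".

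The coding of the 14 items and of question 15 is printed twice in that section, identically. The section then names two scores, the VAS from 0 to 10 with 10 as worst, and "the score for the remaining questions between 15 – 75 (75 is best").

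The planned result is the participants' average score at each of the three time points, leaving out missing values. The author reports finding no information on what size of change is clinically relevant.

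**The concern.** The item coding and the direction label cannot both be right. In every item the larger number is the less desirable answer, so a plain sum must also be worse when it is larger. The label says the opposite.

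The label matters because it is the only statement in the protocol of how the sum score is to be read. There is no threshold for a relevant change, no responder rule and no other sentence on which way the score should move. A reader who follows the label would take a fall in bother as harm and a rise as benefit. That reader would also find the sum score and the VAS pointing in opposite directions for the same clinical change.

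The protocol plans to post the results on a public registry and to submit them for journal publication (Publication of results), and it presents the pilot as the basis for a larger randomised trial. A copied label would carry the inversion into all of these.

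**Working it through.** **Inputs**, all from Statistical considerations:

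- 14 bother items, each coded 1 (best) to 5 (worst)
- 1 closing item, coded 1 (best) to 5 (worst)
- score S = plain sum of the 15 item codes
- stated range 15 to 75, with 75 labelled best
- VAS from 0 to 10, with 10 labelled worst

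**Step 1: reproduce the stated range.**

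- Minimum = 14 × 1 + 1 × 1 = 15
- Maximum = 14 × 5 + 1 × 5 = 75

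Both ends match the protocol, so the score described is the sum of 15 five-point items.

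**Step 2: attach the health states to the ends.**

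| Answers | Sum | State by item coding | State by the label |
|---|---|---|---|
| No bother on all 14 items, question 15 enjoyable | 15 | best | worst |
| Most bother on all 14 items, question 15 terrible | 75 | worst | best |

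The range reproduces. The direction does not.

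**Step 3: look for a reading that rescues the label.**

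- *The VAS counts as one of the 15 questions.* That leaves 14 five-point items and a range of 14 × 1 = 14 to 14 × 5 = 70. This does not match 15–75, and the high end would still be the worst.
- *Each item is reversed as 6 − x before summing.* The score becomes 15 × 6 − S = 90 − S. The best state then scores 90 − 15 = 75 and the worst 90 − 75 = 15. This would make the label true, but the protocol states no reversal anywhere.

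**Step 4: an example of the effect.** Suppose a participant moves from code 4 to code 3 on all 15 items.

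- Before: 15 × 4 = 60
- After: 15 × 3 = 45
- Change: 45 − 60 = −15

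By the item coding this is a 15-point improvement. By the label it is a 15-point deterioration. A matching improvement on the VAS is also a fall, so the two scores agree in fact but conflict under the label.

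**The case against.** Four points can be made on the other side.

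**The averages are not corrupted.** The plan is descriptive. No test, success threshold or composite takes the label as input, so the inversion arises only when someone reads the averages by it. This is correct: the error is in interpretation, not in the data. It does not remove the problem, because the protocol gives no other rule for reading the sum score.

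**An attentive reader has cues.** The VAS direction is stated correctly, the entry criterion puts no xerostomia at 0, and the item codes are printed in the same section. An apparent conflict between the two scores should prompt a check. These cues lower the risk, but they will not help someone who sees only the average score and its label in a results table.

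**The items may have been reversed without the protocol saying so.** The questionnaire is in Danish, was borrowed, and is not reproduced in the protocol. Nothing in the text supports a reversal, and the same coding appears twice, so a slip in the label is the likelier explanation. Still, the documents alone cannot exclude it, and the scoring actually used should be confirmed before the wording is changed.

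**Only one of the two scores is affected, in a small pilot that itself urges great caution in generalising.** The VAS is indeed labelled correctly. But the sum score also serves the main objective, and caution about generalising does not protect against a reversed sign.

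**Conclusion.** The concern holds. As written, the direction label for the sum score contradicts the item coding in the same section. Applied as written, it turns improvement into worsening over the full range of 75 − 15 = 60 points. It affects one of the two scores for the main objective and makes that score appear to disagree with the other.

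The conclusion that 15 is best rests on two assumptions: that the printed coding is the one used for the data, and that the score is the plain sum the protocol describes. If the items were in fact reversed, the label would be right and the protocol would instead be missing the reversal rule. The text must change in either case. Because it concerns the sign of a main outcome, the correction should be made before any result is reported.

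**What to change.** 1. Check against the completed questionnaires and the scoring sheet that answers were entered with the printed codes and added without reversal.
2. If so, change the label in Statistical considerations to: score from 15 to 75, where 15 is best and 75 is worst. No recoding is needed.
3. Add one sentence: on both the VAS and the sum score, a negative change from baseline means improvement.
4. If a reversal was applied, state it explicitly (6 − x for each item), keep 75 as best, and say that the two scores then run in opposite directions.
5. Use the same wording in the registry results posting and in any publication. The registry record was not available for this review, so whether it carries the label is unknown.

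The cost is one or two lines of protocol text and a short check of the scoring. If the printed coding was used, neither the data nor the analysis changes.

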In my project I will use the treatment protocol "Avenue of expression" (5) and a few steps from the protocol "Ten steps protocol"(6) which addresses the areas I expect to develop fibrous tissue after radial therapy and/or surgery in neck or head. The techniques used in these protocols is light (5 grams) manual craniosacral techniques, addressing the fascia in the airway system, the neck, the throat, the meninges and nerve sleeves in the cranium, the visceral cranium, and the soft tissue in the mouth. My rationale in this project is that manual treatment of scar tissue and tissue damaged by radiation will increase mobility and blood flow and therefore possibly increase the production of saliva and decrease the sense of xerostomia.

The manual treatment is combined with home exercises that targets posture in upper body and respiration. This for maintaining the effects of the manual treatment. The homeexercises is inspired by pilates and by knowledge about fascia. (7,8) the exercises are available at this link:

<https://www.[name].dk/oevelser-til-dig-der-lider-af-vejrtraekningsbesvaer-efter-kraeftbehandling/>

Outcome (changes in xerostomia) is measured by a xerostomia questionnaire inspired by the one used in "efficacy of the bioextra dry mouth care system in the treatment of radiotherapy induced xerostomia by Dirix P. Etal(9) The questionnaire used in this project was kindly lent by [name], research manager at Aarhus University Hospital, and is one they (as far as he knows) use for research on this group of patients there.

This project is a pilot project, which will hopefully lay the foundation for a larger project. I have met with [name], research manager at Aarhus University Hospital, who found the project relevant and interesting, but who needed to see more (than just one) patient cases with positive results before he would consider collaborating on a larger randomized trial. This project aims, among other things, to investigate on a slightly larger scale whether craniosacral therapy can create these positive results. If the treatment method used in this project proves to be effective, this project will be the first small steps towards:

1. a larger-scale research project, blinded and randomized and where saliva production measurement is included.

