2. the development of an evidence-based and effective treatment offer for a patient group that currently lacks effective treatment offers and a treatment offer that may be able to complement stem cell therapy in the long term.

Objectives:

Main:

To examine if craniosacral therapy in chest, throat, neck, cranium and mouth , combined with specific exercises, can decrease xerostomia in people who suffer from this after radiation therapy and/or surgery in neck or mouth because of cancer in mouth or throat, by using a questionnaire "xerostomia after minimum 3 months" and comparing baseline results, with results after end of treatment and results 6 months following the last treatment.

Second

To examine if the intervention has any effect on other well-known late sequelae after treatment of cancer in mouth and neck, by asking if and how participants are experiencing these symptoms and comparing baseline results, with results after end of treatment and results 6 months following the last treatment.

Third objective

To examine, if there is any sideeffects or adverse events of the treatment

Design

This project is a pilot-study. It's a one-arm intervention study, with before and after comparisons. There is no masking(open level)

Measurement method

Main objective: The participants will fill in the Danish questionnaire named "Xerostomia questionnaire after minimum 3 months".

The questionnaire will be filled in on the treatment day, before starting the treatment, on the 5.(and last time of treatment, before starting the treatment, and as follow up, 6 month after the treatment.

The participants will be alone, completing the questionnaire.

Other monitoring

Second objective (other late sequelae)

Participants will be contacted by phone the week before starting the treatment and interviewed about, which late sequelae they are experiencing – this will be written down in their journal and will be read aloud so they can confirm. The therapist will ask then about experiencing any changes in the late sequelae mentioned before start of treatment the last time of treatment, and at 6 month following up meeting.

Participants are asked if they are experiencing following late sequelae: dry mouth, obstipation, lymphedema, tinnitus, difficulty swallowing, tense/stiff neck, problems with respiration, stiff jaw, difficulty with speaking, fatigue, difficulty sleeping and pain and mental well-being

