The questionaire will be filled in on the treatmentday, before starting the treatment, on the 5.(and last time of treatment, before starting the treatment, and as a followingup, 6 month after the treatment. The participants will be alone, completing the questionnaire.

The result will be the participants' average score from the 3 times the questionnaire is completed. Averages will be calculated omitting missing values. Unfortunately, I have not been able to find information about, how large a change in the score there is clinically relevant.

Since there is no control group, I have decided that the participants must have completed the treatment at least two years before the start of the trial to ensure that any positive effects on xerostomia and the other side effects are not simply a result of natural healing. This choice was made on the basis of a systematic review of 1366 patients(10), where it is argued that it is probably

at least after 2 years after end of cancer-treatment that a relatively static state with regard to dry mouth occurs.

Because the intervention group is so small, and heterogeneous, when it comes to age, time since treatment, gender and cancer treatment methods results should be generalised to future patient populations with great caution.

During the calculation I have received supervision, from a colleague that has a lot of experience with statistics during research.

Participants:

Inclusion criteria

- More than 18 years, able to consent to participate.
- Have finished radiation treatment and/or surgery for oro-pharyngeal head or neck cancer at least two years before enrolling the project
- They shall score at least 4 on an xerostomia numeric scale where 0 is no xerostomia.

Exclusion criteria

- Persons who by surgery have got both their submandibular saliva glands removed.

And several contraindications:— see below:

- New case of cancer within a year
- Known to have an intracranial aneurysm or 2 close family members (parents, siblings, children) known to have aneurysm or bleeding under the brain.
- Perforation of the dura within a month
- Diagnosed bulge in the medulla oblongata
- History of traumatic neck or head injury that required hospitalization
- Planning to become pregnant, or pregnant before the twelfth week at the start of the project
- Signs of active disease - must be investigated by participant's own doctor first. Sorted out in

this project:

- radiation damage to the cervical vertebrae

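### Available-case averages at each time compare different people before and after treatment if anyone misses a follow-up questionnaire

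*Protocol*

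**What the plan says.** The Design section describes the study in these terms: "It's a one-arm intervention study, with before and after comparisons". The main objective is to be met by "comparing baseline results, with results after end of treatment and results 6 months following the last treatment".

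Under Statistical considerations the questionnaire yields a 0-10 scale score and a sum of 15 items running from 15 to 75 ("This will give two scores"). The questionnaire is completed before the first treatment, before the fifth and last treatment, and six months after treatment. The result is then defined: "The result will be the participants' average score from the 3 times the questionnaire is completed". The missing-data rule follows directly: "Averages will be calculated omitting missing values".

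The Protocol defines no individual change score, does not restrict the averages to people with both values, and does not say that the number contributing at each time will be given. The same section describes the participants: "Because the intervention group is so small, and heterogeneous".

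**The concern.** The text does not say that an average is taken at each time. That is still the natural reading, because a single average pooled over the three times could not show change and so could not serve the main objective. Missing values could also mean unanswered items within a questionnaire; this point concerns whole questionnaires that are missing.

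On that reading, the baseline average covers everyone and each later average covers only those who returned. The difference between them mixes two things: change in the people who stayed, and the fact that the group being averaged is no longer the same. The second part is nobody's change.

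There is no control group, so the before-and-after contrast is the only scored evidence of effect. In a small, heterogeneous group one or two absent people can move an average, which can create an apparent change when nobody changed or hide a real one. The result is also meant to be built on: "This project is a pilot project, which will hopefully lay the foundation for a larger project".

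**Working it through.** **Inputs.** From the Protocol: the one-arm before-and-after design, three questionnaire times, two scores (0-10 and 15-75), and the rule of omitting missing values. The Protocol gives no sample size, standard deviation or dropout rate, so there is no figure of its own to reproduce and those three inputs below are assumptions.

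**Identity.** Let n people have a baseline score and k of them have no follow-up score. Then

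(follow-up mean of stayers) − (baseline mean of all)
= (mean paired change in stayers) + [(baseline mean of stayers) − (baseline mean of all)]
= (mean paired change in stayers) + (k/n) × [(baseline mean of stayers) − (baseline mean of leavers)].

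The last term is the composition term. It is zero if k = 0 or if stayers and leavers have the same baseline mean.

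**Random loss.** The term then has mean zero and standard deviation SD × √(k / (n(n − k))):

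| n, k | Factor | Sum score, SD 5 to 10 | 0-10 scale, SD 1 to 2 |
|---|---|---|---|
| 10, 1 | √(1/90) = 0.105 | 0.53 to 1.05 | 0.11 to 0.21 |
| 10, 2 | √(2/80) = 0.158 | 0.79 to 1.58 | 0.16 to 0.32 |
| 20, 2 | √(2/360) = 0.075 | 0.37 to 0.75 | not computed |

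A simulation at SD 10 gave 1.05, 1.58 and 0.75.

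**Selective loss, sum score.** Take ten invented baseline sums: 30, 34, 38, 40, 44, 46, 50, 52, 58, 58 (mean 45.0, SD 9.63).

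- *Example A, nobody changes.* The 52 and one 58 are missing. Leavers average 55 and stayers 42.5. Difference of averages: 42.5 − 45.0 = −2.5, which equals 0.2 × (42.5 − 55). Mean paired change: 0.
- *Example B, everyone changes by −3.* The 30 and the 40 are missing. Leavers average 35 and stayers 47.5 at baseline, so the stayers' follow-up mean is 44.5. Difference of averages: 44.5 − 45.0 = −0.5, which equals −3 + 0.2 × (47.5 − 35). Mean paired change: −3.0.

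Across all 45 pairs that could be lost from this list with nobody changing, the shift is (90 − sum of the two lost scores)/8. Its mean absolute size is 1.24, its median absolute size is 1.0, 11 of 45 pairs give 2 points or more, and the range is −3.25 to 3.25. Examples A and B are therefore on the large side but not extreme.

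**Selective loss, 0-10 scale.** Take ten invented baseline scores: 5, 5, 6, 6, 6, 7, 7, 8, 9, 9 (mean 6.80). Nobody changes and the two scores of 9 are missing. The follow-up average is 6.25, an apparent change of −0.55 against a paired change of 0.

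**The case against.** The strongest reply is that the problem is conditional. With complete data the difference of averages and the mean paired change are identical, and the Protocol reports no losses. The session-5 questionnaire is filled in at a treatment visit, so anyone attending is likely to have it, and the exposure lies mainly at six months. Under random loss the expected shift is zero and its spread is modest. The examples above are chosen: leavers and stayers differ by 12.5 points, about 1.3 SD, and only 6 of the 45 possible pairs shift by 2.5 points or more. The Protocol also states that no clinically relevant change could be found, so whether such shifts would mislead cannot be settled.

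These points limit the size and the certainty. They do not remove the defect, because the Protocol anticipates missing values by writing a rule for them, and that rule gives the wrong contrast whenever leavers and stayers differ at baseline. A statistical analysis plan that is not shown might add a paired analysis, but the objection is to a rule this document states.

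Participants are also asked in interview about changes in late effects, including dry mouth, at the last treatment and at six months. That is within-person information, but it is not scored and cannot correct the averages. The caution about generalising concerns the small, mixed group and does not address missing questionnaires.

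**Conclusion.** The concern holds. As written, the stated result does not measure within-person change once any questionnaire is missing, unless leavers and stayers happen to have the same baseline mean. This rests on reading the result as one average per time and on baseline being complete.

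The size cannot be fixed from the Protocol. For 2 of 10 people lost and a baseline gap of 0 to 12.5 points between leavers and stayers, the false shift on the sum score is 0 to 2.5 points. Its sign depends on who is missing. The correction should be made, since the contrast carries the study's main conclusion and the remedy uses data already collected.

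**What to change.** For both scores, report the mean within-person change with a 95% confidence interval from baseline to session 5 and from baseline to six months, among people with both values. Beside each, give the number contributing and their baseline mean, next to the baseline mean of all participants. The three averages can stay as description.

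The Protocol's wording suggests that calculation may already have begun ("During the calculation I have received supervision"). If so, add the paired result and label it as added.

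Pairing removes the composition term. It does not remove bias if those who fail to return changed differently from those who did, and the report should say so. Counting a missing follow-up as no change is an optional sensitivity analysis; it is too favourable if the leavers worsened.

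The cost is slightly more analysis and no new data. The estimate may become smaller, larger or less certain; with complete data it is unchanged.

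### The two-year rule is said to rule out natural healing for all late sequelae, but its stated basis is hedged and concerns dry mouth only

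*Protocol*

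**What the plan says.** The Design section describes a "one-arm intervention study, with before and after comparisons", without masking. Under Statistical considerations, the absence of a comparator is answered by an eligibility rule: "Since there is no control group, I have decided that the participants must have completed the treatment at least two years" before the trial starts. Its purpose is given as "to ensure that any positive effects on xerostomia and the other side effects are not simply a result of natural healing".

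The protocol then gives its reason in one sentence. Its first part reads "This choice was made on the basis of a systematic review of 1366 patients(10), where it is argued that it is probably" and it continues "at least after 2 years after end of cancer-treatment that a relatively static state with regard to dry mouth occurs". Reference 10, cited there, is a review of quality of life in survivors of oropharyngeal cancer.

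The second objective is "To examine if the intervention has any effect on other well-known late sequelae after treatment of cancer in mouth and neck", judged by comparing baseline with the end of treatment and with "results 6 months following the last treatment". Under Other monitoring, participants are asked about "dry mouth, obstipation, lymphedema, tinnitus, difficulty swallowing, tense/stiff neck, problems with respiration, stiff jaw, difficulty with speaking, fatigue, difficulty sleeping and pain", and also about mental well-being. They may add any other sequela.

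**The concern.** The rule is expressly offered as a substitute for a control group, and it is claimed to work for xerostomia and for the other side effects together. In context, those other side effects must be the late sequelae of cancer treatment (second objective). Natural healing cannot refer to side effects of the study therapy (third objective).

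The claim outruns its stated support in two ways.

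- **Scope.** The support concerns dry mouth, while the claim also covers swallowing, fatigue, sleep, pain, lymphedema and the rest.
- **Strength.** The claim is a guarantee, while the support is a probability statement about a relatively static state.

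For the second objective, the two-year rule is the only stated safeguard against spontaneous change. Taken at its word, it would let a reader treat an improvement in, say, fatigue or sleep as shown not to be natural course. An open one-arm comparison cannot show that without outside evidence that the symptom is stable. The question has practical weight, because the pilot is meant to lay the ground for a larger randomised study and positive results are to be presented to professionals and patient associations.

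**Working it through.** The protocol has no sample size, error rate or effect size on this point, so there is no figure to reproduce. The check sets the claim beside its basis.

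**Step 1: scope.**

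| | Claim | Stated basis |
|---|---|---|
| Place | Statistical considerations, purpose of the rule | Same section, next sentence |
| Symptoms covered | Xerostomia and the other side effects | Dry mouth |
| Strength | Ensure | Probably; at least; relatively static |

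The sequelae listed under Other monitoring are:

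1. dry mouth
2. obstipation
3. lymphedema
4. tinnitus
5. swallowing
6. neck
7. respiration
8. jaw
9. speaking
10. fatigue
11. sleeping
12. pain
13. mental well-being

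Items listed: 13. Items within the stated basis: 1. Items without a stated basis for stability: 13 − 1 = 12, plus whatever participants add themselves.

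**Step 2: other support in the protocol.** The background section describes a case study of 15 people, on average 8 years after surgery or radiation, with swallowing problems, airway problems and reduced neck mobility. This touches 3 of the 12 items (swallowing, respiration, neck). It shows that such symptoms can still be present years later. It does not show that they are unchanging without treatment after two years. For the other 12 − 3 = 9 items there is not even indirect material.

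**Step 3: strength, for dry mouth itself.** The sentence about two years can be read in two ways:

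- Stability comes no earlier than two years. A two-year minimum then admits people who may not yet have reached it.
- Stability has been reached by two years. The minimum then fits, but the statement is still qualified by *probably* and *relatively*.

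Neither reading supports *ensure*. Both support *less likely*, so the conclusion does not depend on the choice.

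**Step 4: length of the comparison.** For the second objective, baseline is a telephone interview in the week before treatment starts (taken as about 1 week). Five weekly sessions span 5 − 1 = 4 weeks, and follow-up is 6 months after treatment (about 26 weeks). The total is 1 + 4 + 26 = 31 weeks, and 31 ÷ 52 × 12 = about 7 months. That is the period over which a symptom's own course could contribute to the comparison at 6 months. The protocol gives no figure for how much change to expect, so no size of bias can be calculated.

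**The case against.** The best case for the protocol has four parts.

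- **The cited review may cover more than dry mouth.** Its title concerns quality of life, so this is possible. The review is not at hand, so a reader should not infer that the other symptoms are known to change after two years, or that the review fails to support their stability. What stands is narrower: the protocol cites it for dry mouth only and states no other basis.
- **No reporting rule is set.** A reader might infer that every improvement in the other sequelae will be reported as not natural healing. The protocol does not say so. The second objective rests on interviews, with no test, threshold or success criterion. The risk lies in the rationale sentence, not in a prescribed conclusion.
- **The protocol is candid about its limits.** It calls itself a pilot, acknowledges the missing control group and describes the sample as small and heterogeneous, including in time since treatment. This lowers the risk that the pilot is taken as proof. However, its caution concerns generalising to future patients. It does not address whether an observed change is due to treatment, and it leaves *ensure* unqualified.
- **Two years need not be the earliest point of stability.** It is tempting to conclude that a participant just past the limit is probably still improving. The sentence is awkward and can be read otherwise, and the protocol gives no distribution of time since treatment. That stronger reading is not established, and the point does not need it.

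**Conclusion.** The sentence is wrong as written. It gives the two-year rule a property that an open one-arm design does not have and that the stated basis does not supply. By count, 12 of the 13 listed sequelae lack a stated basis for stability. For dry mouth, the basis supports a reduced likelihood of natural healing and no more.

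The count measures how far the stated support reaches. It is not an estimate of bias. The effect is on what the second objective can conclude and, to a lesser degree, on how firmly the main objective can be worded. Data collection, calculations and eligibility are untouched.

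The conclusion rests on two assumptions: that the other side effects in the sentence are the late sequelae of the second objective, and that the protocol's own description of the review is all the support on offer. If a basis for the stability of other sequelae were cited, the scope part would close for those items. The strength part would remain wherever that basis is hedged.

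**What to change.** Under Statistical considerations:

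1. Replace *ensure* with *make less likely*.
2. Say that the stated basis for the two-year rule concerns dry mouth.
3. Add that, without a control group, changes in the other sequelae (second objective) will be reported descriptively and cannot be separated from their natural course, unless a basis for their stability is cited.

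The eligibility cut-off stays as it is. A participant-level table of change in the xerostomia scores by years since treatment is not recommended. It would not bear on the second objective, and in so small a group it would be uninformative.

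The cost is two or three sentences. The downside is a weaker claim for the second objective.
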